#### 6.11.4. Hepatectomy specimen handling and *ex-vivo* MR imaging acquisition

##### 6.11.4.1. Overview.

Intraoperatively, the surgeon will place sutures on the hepatectomy specimen along its anatomic superior and inferior margins. The research technologist will place the specimen in saline in a sealed MR-compatible container and transport the container to the MR3T facility. Using the surgically placed sutures as a guide, the PI and research fellow will re-position the specimen within the container in an attempt to approximate the *in-vivo* anatomic alignment. Non-magnetic material will be used to secure the liver in position. An initial set of images will be obtained and compared to the pre-hepatectomy images on the scanner console.

Through an iterative process, the specimen will be re-imaged and re-positioned until satisfactory alignment with the pre-hepatectomy images is achieved. At this point, high-resolution 1-2 mm thick T1w and T2w images will be obtained of the entire specimen (Section 6.11.4.2) coronal to the scanning table. The PI and research fellow in consensus will review the *ex-vivo* and pre-hepatectomy images together, identify every nodule shown on those images, and, by using surface and intrahepatic landmarks, attempt to co-localize *ex-vivo* nodules and corresponding focal lesions depicted at pre-hepatectomy imaging. The specimen then will be bread-sliced into 5-mm sections sagittal to the scanner table, while leaving a thin rim of tissue intact so that the sections can be kept together.

The sectioned specimen then will be re-imaged in two planes: sagittal to the scanner table (ie, parallel to the cuts) and parallel to the scanning table. Preliminary studies have shown that some saline will fill the space between the sections and be visible as a high-signal intensity film of fluid that delineates the section interfaces on T2w images. The PI, research fellow, and pathologist will review the MR images of the sectioned specimen, number each section consecutively, re-identify the previously detected nodules in both imaging planes, and determine the exact location of each nodule relative to the sections.

After the imaging is completed, the study coordinator will photograph each pathology section in consecutive order. Photographs of both cut surfaces will be obtained and stored in JPEG format.

The study pathologist then will inspect each section grossly and, working together with the PI or radiology research fellow, locate, sample, and submit for histology every nodule detected at *ex-vivo* imaging. Any additional nodules visible on the cut surfaces not identified at *ex-vivo* imaging also will be sampled and submitted for histology. After all nodules are sampled, the tissue will be returned to pathology.

A cross-reference table will be generated of focal lesions depicted at pre-hepatectomy imaging, nodules identified at *ex-vivo* imaging, and nodules confirmed in the pathology specimen. Each lesion or nodule will be given a unique identifier for that subject. Representative screen capture MR images showing the location and identifier of each nodule will be exported in JPEG format.

Each cassette submitted to histology will be labeled with the subject's study identifier and focal lesion identifier. At the pathologist's discretion, some nodules will be sampled and submitted for clinical care; corresponding cassettes will be labeled with clinical identifiers. The processing of cassettes submitted for research will be considered a research expense and will be charged to the study. The processing of cassettes submitted for clinical care will be considered clinical expenses.

6.11.4.2. Specimen imaging.

Protocol details pending

Cardiac coil  
Container  
Localizers  
3D T1w SPGR  
2D T2w FSE  
2D T1w SPGR

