#### **4.0 STUDY OVERVIEW**

In this prospective pilot study, consecutive eligible subjects with CRC metastases to the liver will undergo a research MRI of the liver within 10 days prior to curative hepatectomy done for clinical care. One radiologist will review the MR images and, for each focal lesion (benign or malignant) identified at imaging on each subject, assess 21 imaging features such as size, shape, margination, heterogeneity, kinetic enhancement pattern, and overall confidence for malignancy. Features will include binary, categorical, ordinal, and continuous variables. Sixteen features will be standard and five (T2\*, ADC, shear modulus, late venous phase signal intensity, and hepatocellular phase signal intensity) will be experimental. The MR sequences used to obtain the three quantitative experimental lesion features (T2\*, ADC, shear modulus) will be acquired twice for each subject. After surgery, the hepatectomy specimen will be imaged *ex vivo* at 3T and then sliced into 5-mm sections. Using the *ex-vivo* images as the link, all focal lesions (benign or malignant) detected on the pre-hepatectomy research MR exam or in the resected pathology specimen will be co-localized and submitted for histology. Thus, every lesion detected at pre-hepatectomy imaging will be co-localized on the pathology specimen and every lesion detected on the pathology specimen will be co-localized on the pre-hepatectomy MR images. A board-certified surgical pathologist will review the slides and determine the final histological diagnosis for each lesion. The dichotomized per-lesion histology diagnosis (malignant versus benign) will serve as the per-lesion reference standard. Subjects are expected to have between one and ten CRC metastases in the hepatectomy specimen (average of three) and zero to five benign lesions (average of one). Subjects are not expected to have any malignancies other than CRC metastases.

Number of participants:	30
Recruitment time frame:	18 months
Number of sites:	1
Type of study:	clinical, single-arm, pilot study

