### **6.11.3. Pre-hepatectomy MR imaging interpretation**

#### 6.11.3.1. Overview.

The study radiologist will have expertise in MRI of the liver. The radiologist will be trained on a test set to become familiar with the imaging criteria. After the training, the radiologist will review and interpret the pre-hepatectomy research exams. The radiologist will know the subject's study ID and date of birth, and will be aware that the subject has a pre-operative diagnosis of CRC metastasis to the liver. The coordinator will explain to the radiologist the segment(s) that were resected at surgery. The radiologist will be blinded to all other information. MR images (test set and research exams) will be reviewed on high-resolution >4 megapixel gray-scale monitors using the hospital PACS system.

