**6.12. Histology analysis**

Slides will be stained (haemotoxolin and eosin, trichrome, Prussian blue) at a histology lab. The study pathologist will review the slides and issue a dichotomous histological diagnosis for each submitted nodule (malignant or benign). Photographs of representative histology slides will be taken. One unstained slide will also be obtained as a precaution.

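### The specimen sampling rule in 6.11.4.1 omits lesions in the resected liver seen only on the pre-hepatectomy MRI, although 4.0 promises them histology and 9.1.1 and 9.2 analyse them against it

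*Protocol*

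**What the plan says.** Section 4.0 states that all focal lesions "detected on the pre-hepatectomy research MR exam or in the resected pathology specimen will be co-localized and submitted for histology". It then draws the consequence without exception: "Thus, every lesion detected at pre-hepatectomy imaging will be co-localized on the pathology specimen".

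Section 9.1.1 includes in the analysis any lesion identified at pre-hepatectomy imaging, ex-vivo imaging, pathology or a combination of these, and names the dichotomized histology as each lesion's reference standard. The primary-aim analysis plan in 9.2 defines true and false positives and negatives by histology.

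The working instruction in 6.11.4.1 covers two groups. The pathologist, with the PI or fellow, is to "locate, sample, and submit for histology every nodule detected at" ex-vivo imaging. The second group begins "Any additional nodules visible on the cut surfaces not identified at" ex-vivo imaging, and these are sampled as well. The next step is "After all nodules are sampled, the tissue will be returned to pathology". Section 6.12 gives a diagnosis only to nodules that were submitted.

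Section 6.13 anticipates the remaining lesions. A lesion called by the radiologist, not visible ex vivo and not found at pathology, is to be counted as a false negative imaging finding.

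**The concern.** The overview and the working instruction disagree on which lesions go to histology. The difference falls on lesions seen only on the pre-hepatectomy MRI, and their true status decides whether the MRI call was right or wrong. If 6.11.4.1 is followed as written, these lesions enter the primary analysis with a label set by rule, which is not the reference standard that 9.1.1 states. A small metastasis with no visible correlate and a call with nothing behind it would be treated alike.

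Such lesions are plausible on the protocol's own terms. The ex-vivo sequences listed in 6.11.4.2 (details pending) are T1- and T2-weighted only. The in-vivo examination adds diffusion, elastography, dynamic, late venous and hepatocellular series. Late venous and hepatocellular signal intensity, ADC and shear modulus are among the experimental features that secondary aim 1 sets out to test.

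**Working it through.** **Text comparison**

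| Lesion in resected liver, seen on | Histology under 4.0 | Sampled under 6.11.4.1 | In analysis (9.1.1) | Status comes from |
|---|---|---|---|---|
| Ex-vivo imaging, with or without MRI | yes | yes | yes | histology |
| Cut surface, with or without MRI | yes | yes | yes | histology |
| Pre-hepatectomy MRI only | yes | no | yes | default in 6.13 |

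Only the last row is inconsistent. In 6.11.4.1 the PI and fellow review both image sets, "identify every nodule shown on those images", and attempt to match them. The later sampling sentence still reaches only ex-vivo and cut-surface nodules.

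A lesion flagged only by the study radiologist has no other route to tissue. Section 6.11.3.1 says "The coordinator will explain to the radiologist the segment(s) that were resected at surgery", which suggests a read after surgery, and no step passes the radiologist's list to the specimen team. That list is first set against the specimen findings in 6.13.

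**Size**

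Inputs from the protocol: 30 subjects, with on average three metastases and one benign lesion each (4.0, 9.1.1). This gives 30 × 3 = 90 metastases and 30 × 1 = 30 benign lesions, 120 in all.

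Assumptions, none of them in the protocol:
- Sensitivity is 80% (72/90) and specificity is 80% (24/30) on verified lesions.
- There are u = 6 or 12 MRI-only calls, i.e. 6/120 = 5% or 12/120 = 10%, all feature-positive.
- Tissue would show one third of them (2 or 4) to be metastases.

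*Default scores them as non-metastases.* Specificity = 24/(30 + u):
- u = 6: 24/36 = 66.7%
- u = 12: 24/42 = 57.1%

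With tissue, only the remaining two thirds count as benign, so specificity = 24/(30 + 2u/3):
- u = 6: 24/34 = 70.6%, a change of 3.9 points
- u = 12: 24/38 = 63.2%, a change of 6.0 points

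*Default scores them as false negatives, as 6.13 literally says.* Sensitivity = 72/(90 + u), with specificity unchanged at 80%:
- u = 6: 72/96 = 75.0%
- u = 12: 72/102 = 70.6%

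With tissue, the one third would be true positives, so sensitivity = (72 + u/3)/(90 + u/3):
- u = 6: 74/92 = 80.4%
- u = 12: 76/94 = 80.9%

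*Lesions left out.* Both estimates stay at 80%.

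For scale, the unclustered 95% half-width for 24/30 is 1.96 × √(0.8 × 0.2/30) = 14.3 points.

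**The case against.** The strongest reply is that the specimen work-up already looks hard for lesions seen on the pre-hepatectomy MRI. The PI, a liver radiologist according to 10.1, and the fellow compare the two image sets at 1–2 mm ex-vivo resolution. With the pathologist they then locate nodules on the sectioned specimen before sampling, and the cross-reference table covers lesions depicted at pre-hepatectomy imaging. This stands, and it should keep the number of MRI-only lesions down. It does not put a lesion that still lacks a correlate on the sampling list.

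Three stronger readings are tempting, and the protocol does not support them:

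- **That the tissue is lost.** It is returned to pathology, which is not the same as discarded. The review in 6.13 also uses the archived ex-vivo images, so a call made only by the study radiologist can still be searched for on them. What the protocol lacks is a step for sampling tissue at that stage.
- **That the read takes place after surgery.** This is inferred from a past tense in 6.11.3.1. No read date is given, and the contradiction between 4.0 and 6.11.4.1 does not depend on it.
- **That missing histology cuts specificity from 80% to 67% or 57%.** Those falls come from adding unmatched calls to the denominator and scoring them as false positives. The part due to missing tissue is the 4 or 6 points shown above, well inside the sampling error of a study this size. The default in 6.13 also says false negative, which moves sensitivity instead.

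It is also fair to say that sampling a mapped site with no visible target may miss the lesion.

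**Conclusion.** The contradiction is real. As written, 6.11.4.1 leaves a lesion in the resected liver that is seen only on the pre-hepatectomy MRI without the histology that 4.0 promises and 9.1.1 and 9.2 require. Section 6.13 then labels it by default. That conclusion rests on the text alone.

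The size is uncertain because the number of such lesions is not given. Under the assumptions stated, the effect on specificity is about 4 to 6 points if the default means non-metastasis. If the false-negative label is taken literally, sensitivity falls from 80% to 75% or 71%. That label does not fit 9.2, where a false negative needs a negative feature and malignant histology, so 6.13 and 9.2 need to be reconciled too.

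A reader might infer that the study read has to be completed before surgery and handed to the specimen team. The contradiction does not require this. It would conflict with 6.11.3.1, where the radiologist is told which segments were resected, and it would let the calls under test steer the sampling for the reference standard.

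**What to change.** 1. Amend 6.11.4.1. Before the tissue is returned, also submit for histology the mapped section location of every lesion identified on the pre-hepatectomy images in the PI and fellow's review that lies within the resected liver and has no ex-vivo or gross correlate.
2. Restrict the default in 6.13 to lesions still without a correlate after that sampling, including any called only by the study radiologist. Flag them as not histologically verified, and state which cell of the 9.2 table they enter.
3. Report sensitivity and specificity with and without the flagged lesions.
4. Qualify the sentence in 4.0 so that it matches the amended rule.

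The cost is protocol wording and a few extra research cassettes, which 4.0 already implies. No added procedure on the subject and no change to the reading schedule are needed. The limitation is that a benign result at a mapped site may reflect a sampling miss, so such results should be identifiable in the reference standard table.

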**6.11.5. Imaging archival**

MR images (pre-hepatectomy or *ex vivo*) will be saved in DICOM format. Screen capture images will be saved in JPEG format.

**6.12. Histology analysis**

Slides will be stained (haemotoxolin and eosin, trichrome, Prussian blue) at a histology lab. The study pathologist will review the slides and issue a dichotomous histological diagnosis for each submitted nodule (malignant or benign). Photographs of representative histology slides will be taken. One unstained slide will also be obtained as a precaution.

## **7.0 DATA COLLECTION AND MANAGEMENT**

The PI will supervise the data collection and management. The following types of data and materials will be collected:

### **7.0.1. Regulatory**

A research chart will be created for each subject. The chart will include the signed consent form, a copy of the subject's experimental bill of rights, and a signed HIPAA form. Research charts will be kept in locked file cabinets.

An enrollment log will be maintained. The enrollment log will confirm that informed consent was obtained on each subject.

### **7.0.2. Parametrized data**

Standardized data entry forms will be designed for each type of data being collected:

- Subject identifiers and demographics
- Subject lab results (e.g., eGFR, urine pregnancy test)
- List of sequences acquired and repeated during the pre-hepatectomy examination
- Adverse events occurring during the MRI appointment
- Adverse events occurring during first 24 hours after Gd injection as recorded by the study surgeon at subject admission for surgery.
- Lesion cross reference table
- Lesion reference standard table
- MRI features for each lesion

The research coordinator or study investigator will manually enter data into the corresponding data forms. Completed data entry forms will be duplicated. One set will be kept with each subject's research chart. One set will be kept in folders with other forms of the same type. The coordinator will transfer the data from the entry forms into an electronic database. The database is password protected, maintained by a data manager at the MR3T facility, stored on two servers, backed up to external hard-drives every 24 hours.

For statistical analysis, the database program will generate de-identified spreadsheet reports containing the variable of interest to the study statistician.

### **7.0.3. Images**

Several types of images will be collected:

- MR images in DICOM format
- Screen-saved MR images in JPEG format
- Photographs of pathology sections in JPEG format.
- Photographs of histology specimens in JPEG format (select lesions)

DICOM format images will be stored on the hospital's password-protected PACS system. JPEG format images will be stored on two separate password protected hard-

drives in the MR3T facility. All images (DICOM or JPEG) will also be stored on CD in duplicate. Duplicated CDs will be kept in separate locked cabinets in the MR3T facility.

**7.0.4. Histology slides and tissue blocks.**

Histology slides and tissue blocks will be labeled with the subject ID and lesion ID and stored in a locked histology filing cabinet in the MR3T facility. Blocks will be kept as a precaution in case slides are damaged or lost.

## **8.0 ADVERSE EVENTS PROCEDURES**

### **8.1. Definition of Adverse Events and Potential Risks**

An **Adverse Event (AE)** is any untoward medical occurrence in a participant that does not necessarily have a causal relationship with the study intervention. An AE can therefore be any unfavorable and unintended sign (including an abnormal laboratory or physiological finding), symptom, or disease temporally associated with the use of a medical treatment or procedure, regardless of whether it is considered related to the medical treatment or procedure (attribution of unrelated, unlikely, possible, probable, or definite).

### **8.2. Definition of Serious Adverse Events (Serious Adverse Events List)**

A **Serious Adverse Event (SAE)** is defined as any untoward medical occurrence that:

- results in death, or
- is life-threatening (at the time of the event), or
- requires inpatient hospitalization or prolongation of an existing hospitalization, or
- results in persistent or significant disability or incapacity, or
- is a congenital anomaly/birth defect.

### **8.3. Adverse Events Characteristics**

#### **8.3.1. Grading of Adverse Events**

Grade is used to denote the severity of the adverse event.

- 1 – Mild
- 2 – Moderate
- 3 – Severe
- 4 – Life-threatening or disabling
- 5 – Fatal

#### **8.3.2. Definition of Expected**

MRI Scan

- Anxiety/Stress;
- Claustrophobia;
- Discomfort.

Contrast Agent (MultiHance)

- Nausea;
- Headache;
- Hives;
- Temporary low blood pressure;
- Allergic reaction.

Expected Adverse Events from Needle Placement

- Minor discomfort;

- Bleeding;
- Infection;
- Bruising.

### **8.3.3. Attribution of Adverse Events**

Attribution of the AE:

- **Definite** – The AE is clearly related to the study treatment.
- **Probable** – The AE is likely related to the study treatment.
- **Possible** – The AE may be related to the study treatment.
- **Unlikely** – The AE is doubtfully related to the study treatment.
- **Unrelated** – The AE is clearly NOT related to the study treatment.

## **8.4. Adverse Event Documentation and Reporting**

### **8.4.1. Assignment of attribution and grades**

The PI will assign the grade and attribution for each AE/SAE.

### **8.4.2. Documentation**

The PI will document all Adverse Events (AEs) that within the first 24 hours following contrast injection. This time period exceeds 10 elimination half-lives of gadobenate dimeglumine [MulthiHance product insert]).

AEs will be recorded within the study participant's chart within one week of the PI becoming aware of the event. The nature of each event, date and time (when appropriate) of onset, outcome, frequency, maximum intensity, action taken, and attribution will be recorded.

### **8.4.3. Expedited or Routine Adverse Event Reporting**

#### **8.4.2.1. Definitions**

**Expedited reporting** is defined as immediate notification of the IRB within the specified timeframe outlined in the protocol. Routine reporting requirements also apply.

**Routine reporting** is defined as documentation of adverse events on source documents and submission to the local IRB.

#### **8.4.2.1. Instructions**

1. Grade 3 unexpected adverse events with hospitalization that are possible, probable, or definite require a complete SAE report to be submitted within **10 calendar days** of first knowledge of the event. **Routine reporting procedures also apply.**
2. Grade 3 expected adverse events with hospitalization that are possible, probable, or definite will be reported by **routine reporting procedures only.**

3. Grade 3 unexpected and expected adverse events without hospitalization that are possible, probable, or definite will be reported by **routine reporting procedures only**.
4. Grade 4 unexpected and expected adverse events that are possible, probable, or definite require a complete SAE report to be submitted within **10 calendar days** of first knowledge of the event. **Routine reporting procedures also apply**.
5. Grade 5 unexpected and expected adverse events that are possible, probable, or definite will be reported via phone report within a **24-hour** time period to the IRB by the investigator or investigator-designee. In addition, a complete SAE report is due to the IRB within **10 calendar days** of the initial 24-hour telephone report. **Routine reporting procedures also apply**.
6. Expedited adverse event reporting must be completed within 10 working days of first knowledge of the event.

## **9.0 STATISTICAL CONSIDERATIONS**

### **9.1 Study Design and Endpoints**

#### **9.1.1. General study design.**

This is a prospective cohort pilot study assessing 3T MRI for diagnosis of CRC metastases to the liver in pre-hepatectomy patients. Consecutive eligible subjects with CRC metastases to the liver will undergo a research MRI of the liver within one week prior to curative hepatectomy done for clinical care. One radiologist will review the MR images and, for each focal lesion (benign or malignant) identified at imaging on each subject, assess 21 imaging features such as size, shape, margination, heterogeneity, kinetic enhancement pattern, and overall confidence for malignancy. Features will include binary, categorical, ordinal, and continuous variables. Sixteen features will be standard and five (T2\*, ADC, shear modulus, late venous phase signal intensity, and hepatocellular phase signal intensity) will be experimental. The MR sequences used to obtain the three quantitative experimental lesion features (T2\*, ADC, shear modulus) will be acquired twice for each subject. The radiologist also will assess two-per patient imaging features (abdominal AP diameter at the level of the portal vein bifurcation and the presence of ascites). Three demographic features (subject age, gender, ethnicity) will be available for the multivariate analyses; of the three, age will potentially be known to the radiologist as the scans will include the subject's date of birth.

For each subject, the lesions included in the analysis will be those identified at pre-hepatectomy imaging, *ex-vivo* imaging, pathology, or any combination of the three. The reference standard for each lesion will be the dichotomized histological diagnosis (malignancy versus other). Subjects are expected to have between one and ten CRC metastases in the hepatectomy specimen (average of three) and zero to five benign lesions (average of one). Subjects are not expected to have any malignancies other than CRC metastases.

